14.2 Subject Treatment Discontinuation Procedure

When a subject discontinues participation in the clinical trial, the following procedure should be used.

- The investigators should enter the date of discontinuation, reason for discontinuation, AE incidence status, and drug therapy status in the eCRFs. To ensure the safety of discontinued subjects, all possible measures should be taken, appropriate treatment should be given, and also for the safety after discontinuation, perform follow-up investigation as much as possible.
- If a subject discontinued the trial due to a safety issue arise from an incidence of AE or worsened disease, the investigators enter it in the eCRF in accordance with Section 11 "ADVERSE EVENTS."
- If an AE is found at the time of discontinuation, the investigators should perform a follow-up investigation of the AE.
- The investigators should promptly inform the sponsor of the subject's treatment discontinuation.

14.3 Follow-up Investigation of Subjects with Missing Visits

If a subject miss the follow-up observation as specified in the protocol because the subject failed to visit, the investigators should contact the subject as much as possible to investigate the subject's health condition (confirmation of survival, the presence or absence of an AE). In such a case, enter the contact means, date of contact, subject's condition, and the reason for missing visit in the eCRF. When after trying to contact to the subject, but the subject could not be reached, enter the fact, date of contact, contact means the eCRF.

15 STATISTICAL ANALYSIS

15.1 Safety and Efficacy Analysis of EWJ-003

In this clinical trial, the safety and efficacy of EWJ-003 will be evaluated in subjects for whom the investigational valve was dilated at a nominal volume. Subjects in the bailout treatment registry in whom the THV could not be dilated at a nominal volume will not be included in the analysis set (see Section 15.2 "Bailout Treatment Registry Statistical Analysis"). Also subjects enrolled in the continued access registry will not be included in the analysis set for the safety and efficacy evaluation of EWJ-003 (see Section 15.3 "Statistical Analysis of the Continued Access Registry").

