Bailout Treatment Registry	
In this trial, a subject who received valve implantation with non-nominal balloon inflation volume as a result of the medical judgment will be considered "bailout subject" and registered to the Bailout Treatment Registry at the end of the study procedure. Bailout subjects will not be counted as the study target population (30 subjects), so that they will be excluded from the analysis population to evaluate the safety and effectiveness of EWJ-003. Post-procedure follow-up for them is the same as subjects with nominal valve implantation.
 <pre> graph TD A[Informed consent] --> B[Screening] B --> C[Case review] C --> D[Enrollment] D --> E[Index procedure] E --> F[Dilatation at a non-nominal volume] E --> G[Dilatation at a nominal volume] F --> H[Bailout Treatment Registry] G --> I[EWJ-003 analysis set (30 subjects)] H --> J[Safety and efficacy evaluation (at 1 year post-procedure)] I --> J J --> K[Follow-up until at 5 years post-procedure] </pre>
Study sites	Maximum 3 sites in Japan
Study procedure	
TF Approach
 
 Using the crimper, crimp the THV on the valve crimping site of the delivery system after the THV rinsing. Puncture the iliac-femoral artery by the standard procedure, and advance the guidewire to the left ventricle. Advance the balloon catheter from the femoro-iliac artery, and predilate the stenosed native aortic valve under the rapid pacing. As maintaining guidewire position, remove the balloon catheter and subsequently expand the access site by using the introducer to place the introducer sheath. Insert the delivery system through the sheath and advance it until descending aorta. Initiate valve alignment by pulling the balloon shaft of delivery system, and transfer the THV on the balloon. Then advance the THV until the predilated native aortic valve.

Item	Content

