4 STUDY DESIGN

4.1 Study Design

This clinical trial is a prospective, open, non-randomized, multi-center, single arm study.

This trial evaluate the safety and efficacy of EWJ-003 in patients who were deemed medically inappropriate for sAVR and EWJ-003 therapy would be the best treatment available by the heart team, among chronic dialysis patients with symptomatic severe AS. Since the standard therapy of chronic dialysis patients with symptomatic severe AS is sAVR, the performance goal (PG) will be set based on the clinical research results of sAVR in chronic dialysis patients, and non-inferiority of this clinical trial results of EWJ-003 to the standard therapy will be verified.

In this clinical trial, patients in whom deployment of the THV by balloon dilatation at a nominal volume was impossible for a medical reason during study procedure will be regarded as bailout cases, and these cases will be included in the bailout treatment registry at the end of the study procedure. The bailout cases will be enrolled separately from the target sample size of this trial, and will not be included in the analysis set for the safety and efficacy evaluation of EWJ-003.

In this clinical trial, on humanitarian grounds, subject enrollment will be continued as an continued access until EWJ-003 gains marketing approval, so that the subjects will be able to receive EWJ-003 therapy continuously even after completion of subject entry into the EWJ-003 analysis set. For the continued access registry, see Section 4.4.

[figure not shown]

Figure 4-1: Study design of this clinical trial

<Rationales for the setting>

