7.4 Bailout Treatment Registry

Patients in whom deployment of the THV by balloon dilatation at a nominal volume was impossible for a medical reason will be regarded as bailout cases, and these cases will be included in the bailout treatment registry at the end of study procedure. The bailout cases will be enrolled separately from the target sample size of this trial (30 subjects), and will not be included in the analysis set for the safety and efficacy evaluation of EWJ-003. The same post-procedural follow-up observation will be performed as that for subjects with successful valve implant procedure at a nominal volume, and the follow-up observation will be performed for up to 5 years post-procedure.

In the continued access registry, irrespective of whether the THV was implanted at a nominal volume or not, subjects who received the study procedure will be included in this registry.

- 65 -

[figure not shown]

Figure 7-1: Bailout treatment registry treatment flow

- 66 -

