14 SUBJECT TREATMENT DISCONTINUATION

14.1 Subject Treatment Discontinuation

Enrolled subjects will continuously participate in the clinical trial until all follow-up observations specified in the protocol are completed. However, the following subjects should discontinue the trial.

- A subject or the legal representative requests discontinuation of the participation in the clinical trial.
- The principal investigator or subinvestigators judges that continued trial will be a disadvantage for subject's health condition.
- The study procedure has not been started.
- When the subject is exiting the operation room, the investigational valve has not been implanted.
- The investigational valve was removed.
- The subject died.
- Continued participation in the clinical trial was deemed difficult.
- The sponsor requests (continued trial was determined to be a disadvantage in the subjects).

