15.1.1.2 As-treated analysis set

A subject population consisting of subjects who were enrolled in this clinical trial and implantation of the study device was initiated is defined as as-treated (AT) analysis set. The time when invasion such as incision was made on the access site is regarded as the start of the study procedure. The primary endpoint and secondary safety and efficacy endpoints will be analyzed in the AT analysis set.

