15.1.2 Statistical analysis plan and statistical method

Mortality at 1 year post-procedure, the primary endpoint, will be analyzed in the AT analysis set to verify the non-inferiority of EWJ-003 therapy to the standard therapy. The non-inferiority test will be performed

- 104 -

made and reasons for the changes, and the Statistical Analysis Plan should be revised.

All deviations from the Statistical Analysis Plan should be described in the Study Report.

- 106 -

using one-sided Fisher's exact test, and at one-sided significant level of 0.05 if the 95% CI upper limit for the mortality at 1 year post-procedure is lower than the PG (45%), non-inferiority of EWJ-003 therapy to the standard therapy would be verified.

No statistical tests will be conducted for the secondary endpoints, but evaluate by descriptive statistics. The secondary valve performance endpoints based on the echocardiographic evaluation will be analyzed in the VI analysis set, and other secondary endpoints. Other data including subject background and baseline characteristics, and procedure information, etc. will be summarized by descriptive statistics.

All statistical analyses will be performed for, in addition to the entire analysis sets, each approach of TF, TA, and TAO. For continuous variables, the number of measurements, mean, standard deviation, median, quartile, minimum, maximum, and 95% CI of the mean will be calculated. On the other hand, for categorical variables, the number of samples (n), percentage (%), and for binary variables 95% CI will be calculated. For the primary endpoint and secondary safety and efficacy endpoints, the cumulative incidence will be calculated by Kaplan-Meier estimates as needed.

The detailed statistical analysis plan and statistical method are included in the Statistical Analysis Plan.

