Enrolled subjects	Enrollment in this clinical trial should be completed by the document describing the patient's eligibility finally determined by case review. Enrollment in the continued access registry should be completed by the start of the study procedure at the	

Term	Definition	Reference/rationale																																			
	time point when an invasion such as an incision is made on the access site).																																				
Bailout subjects	Patients in whom deployment of the THV by balloon dilatation at a nominal volume was impossible for a medical reason will be regarded as bailout cases.																																				
Valve explants	Removal of the implanted investigational valve for any reason. (See "Re-operation")	STS/AATS																																			
Length of post-procedural hospitalization	A period from the day of study procedure to hospital discharge.																																				
Study procedure	Study procedure refers to the procedure using the study device specified in the protocol for this clinical trial. The time of the start of the study procedure is the time after a subject's entering the operation room when invasion such as incision was made on the access site, and the time when closing the access site such as incision site was completed should be regarded as the end of study procedure.																																				
Infections	Known infections that require intravenous administration of antibiotics for reasons other than prophylactic use or prolonged hospitalization.																																				
Intent-to-treat (ITT) analysis set	Regardless of whether or not the study procedure was given, or whether or not the study device was implanted, the intent-to-treat (ITT) analysis set is defined as an analysis population consists of all subjects enrolled in this clinical trial.																																				
Past medical history	History of a disease, disorder, etc. that had developed before the start of the study procedure and resolved at the start of the study procedure.																																				
Mitral valve tissue damage or dysfunction	Damage to the mitral valve tissue (chorda tendinae, papillary muscles, or cusp) or dysfunction (limitation posed by the investigational valve) newly found during or after the study procedure in the angiogram or echocardiography findings.	VARC-2																																			

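### The primary 1-year mortality test leaves out bailout subjects, a status fixed only at the end of the procedure, and the supplied text plans no all-treated result beside it

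*Combined protocol and SAP*

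**What the plan says.** - **Enrollment comes first.** The Glossary entry for enrolled subjects reads "Enrollment in this clinical trial should be completed by the document describing" the eligibility finally decided at case review. Section 5.4 says the same. Both place enrollment before the procedure.
- **Bailout status comes last.** Section 7.4 says that "these cases will be included in the bailout treatment registry at the end of study procedure". The Synopsis and Section 4.1 give the same timing.
- **Bailouts are left out.** The opening sentence of Section 15.1 says that "the safety and efficacy of EWJ-003 will be evaluated in subjects for whom the investigational valve was dilated at a nominal volume". Its next sentence removes bailout registry subjects from the analysis set. The Synopsis adds that they do not count toward the 30.
- **The set named for the test does not mention this.** Section 15.1.1.2 and the Glossary define the as-treated (AT) set as "subjects who were enrolled in this clinical trial and implantation of the study device was initiated". Section 15.1.2 says that the primary endpoint "will be analyzed in the AT analysis set to verify the non-inferiority of EWJ-003 therapy to the standard therapy".
- **Other sets.** Section 15.1.1.1 defines an intent-to-treat set, but no endpoint is assigned to it. Section 15.2 analyses bailouts separately and without a test.
- **Bailout wording differs.** The Synopsis describes "a subject who received valve implantation with non-nominal balloon inflation volume as a result of the medical judgment". Section 4.1 describes "patients in whom deployment of the THV by balloon dilatation at a nominal volume was impossible for a medical reason during study procedure", and Section 7.4 and the Glossary follow it.

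Section 15.1.2 refers to a separate, more detailed Statistical Analysis Plan, which is not among the documents supplied.

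**The concern.** Bailout status is not a baseline characteristic. It is assigned after enrollment, after access and after the attempt at deployment, so it is partly an outcome of the treatment under test. Leaving these subjects out means that the group tested is not the group enrolled and treated. If subjects whose deployment went badly also die more often, the tested group looks better than the treated group. If they do no worse, little is lost.

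The trial has a single arm and about 30 subjects, and the result is compared with a fixed 45% goal. One or two subjects can therefore decide a result that lies near the boundary. The stated conclusion is about EWJ-003 therapy, not about therapy given deployment at nominal volume, and no planned figure lets a reader see whether the distinction matters.

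**Working it through.** **Inputs from the documents.** Performance goal 45%, predicted mortality 20%, one-sided α = 0.05, 24 subjects for 81.1% power, target 30 (Sections 4.2 and 4.3). **Assumed, because the documents do not give them:** 30 subjects in the primary set, k = 1 to 4 bailouts in addition, and bailout 1-year mortality of 20%, 30%, 45% or 60%.

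**1. The plan's own figure.** Pass if deaths X ≤ c, where c is the largest count with P(X ≤ c | n, 0.45) ≤ 0.05. For n = 24, P(X ≤ 6) = 0.0364, so c = 6. Power is P(X ≤ 6 | 24, 0.20) = 0.8111, which reproduces 81.1%. The figure is that of a one-sample exact binomial test.

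**2. Cut-offs with bailouts added.** The exact upper limit U for x deaths in n solves P(X ≤ x | n, U) = α; that is, U is the 1 − α quantile of Beta(x + 1, n − x). Section 15.1.2 names both a one-sided 0.05 level and a 95% limit, so both readings are shown.

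| n | 30 | 31 | 32 | 33 | 34 |
|---|---|---|---|---|---|
| Most deaths that pass, one-sided 95% | 8 | 8 | 9 | 9 | 10 |
| Most deaths that pass, two-sided 95% | 7 | 8 | 8 | 8 | 9 |

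**3. Where the verdict changes.**
- One-sided, pass to fail: 8/30 gives 43.0%. One bailout who dies makes 9/31, 45.2%. At 7/30 it takes three bailouts who all die: 10/33, p = 0.062.
- One-sided, fail to pass: 9/30 gives 46.5%. Two surviving bailouts make 9/32, 43.9%. At 10/30 it takes four survivors: 10/34, 44.8%.
- One-sided, no change: at 6/30 the worst case with four bailouts is 10/34, 44.8%, still a pass.
- Two-sided: 7/30 passes (42.3%) but 9/32 fails (46.75%); 8/30 fails (45.9%) but 8/31 passes (44.6%). Here 6/30 is not quite immune: three bailouts who all die make 9/33, one over the cut-off of 8.

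The sensitive zone is thus about 7 to 9 deaths in 30, an observed mortality of 23% to 30%. It is the upper limit, not the observed rate, that lies near 45%.

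**4. How often the two results would disagree.** Take X ~ Bin(30, 0.20) and B ~ Bin(k, m) independent, with m the bailout mortality. Compare X ≤ c(30) with X + B ≤ c(30 + k).

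| | Primary passes, all-treated fails | Primary fails, all-treated passes |
|---|---|---|
| One-sided | 0.3% to 10.5% | 0% to 7.0% |
| Two-sided | 0% to 13.8% | 0.7% to 11.8% |

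The left-hand maxima need three bailouts at 60% mortality. The right-hand maxima arise with four bailouts at 20%, the same mortality as everyone else. They reflect a larger n and a discrete cut-off, not bias.

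**5. False-pass illustration.** Suppose that all-treated mortality is exactly 45% and a share f are bailouts with mortality q. Nominal-volume mortality is then (0.45 − f·q)/(1 − f). With f = 0.10 and q = 0.60 this is 0.39/0.90 = 0.433, and P(X ≤ 8 | 30) rises from 3.1% to 4.6%. With q = 0.80 it is 7.5%. With q below 0.45 it falls under 3.1%.

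**The case against.** **The exclusion is open and consistent.** The Synopsis and Sections 4.1, 7.4, 15.1 and 15.2 all state it. The use being evaluated is deployment at the nominal volumes of Table 3-2. Bailouts have the same 5-year follow-up and are reported separately, so a reader could pool the counts. This stands as an answer to any suggestion of concealment, and it is why the primary test need not change. It does not make the tested group the treated group. Nor does it say what is concluded about EWJ-003 therapy if the two disagree.

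**The separate Statistical Analysis Plan may already contain the analysis.** This also stands. The point is limited to the supplied text.

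**A stronger reading: deaths and conversions before deployment drop out too.** A reader might infer this from the opening sentence of Section 15.1, or infer from the Section 4.1 wording that a conversion is a bailout. Read together, the documents do not support it:
- Section 15.1.1.2 takes access incision as the start of the procedure and sets no deployment condition.
- Section 15.1.1.3 removes conversions to surgery by name, but only from the valve implant set.
- The second sentence of Section 15.1 names bailouts, not deaths or conversions.
- Section 14.1 lists "When the subject is exiting the operation room, the investigational valve has not been implanted" as a discontinuation, and Section 4.3 does not replace discontinued subjects, so they stay among the 30.
- Section 7.3 ends required follow-up for a converted subject, while Section 7.4 gives a bailout five years. One subject cannot be under both rules.

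What is left there is loose wording.

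**A second stronger reading: the exclusion favours the device.** The documents give no bailout rate or bailout mortality, so no direction can be claimed.

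**Conclusion.** The point holds in a bounded form and is worth fixing. Subjects are removed from the primary mortality test after enrollment, by a status that depends on the procedure, while the conclusion is drawn for the therapy as a whole and no all-treated mortality result is planned in the supplied text.

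The practical size is small unless the trial lands near its boundary. At the planned result of 6/30, up to four bailouts cannot change the one-sided verdict; at 8/30 a single bailout death does. The disagreement percentages rest entirely on assumed bailout numbers and mortality and on 30 subjects at 20%. They show what could happen, not an estimate of bias. The stated sample size and power are not in question.

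**What to change.** 1. **Add one supportive analysis to Section 15.1.2:** 1-year mortality in all main-trial enrolled subjects with access started, bailouts included, with the same exact upper limit shown against 45%. The primary test and its decision rule are unchanged. If the two results disagree, limit the conclusion in Section 15.1.2 to nominal-volume deployment. Record in the Section 15.4 revision history whether this was added before outcomes were known, or cite the separate Statistical Analysis Plan if it already provides it.
2. **Align the wording.** State in Sections 15.1 and 15.1.1.2 and in the Glossary that the AT set excludes only bailout registry subjects, and that deaths and conversions before deployment stay in it. Reconcile, for analysis purposes, the bailout definitions in the Synopsis, Sections 4.1 and 7.4 and the Glossary.

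**Cost.** One table and a few sentences. Bailouts are already followed for five years (Section 7.4), and reported deaths to 1 year are adjudicated for all enrolled subjects (Section 13.1). The extra effort is to seek 1-year vital status for converted subjects, whose required follow-up ends under Section 7.3, although Sections 10.2.9 and 14.2 already ask for follow-up after discontinuation where possible. Main-trial enrollment is closed, so the added analysis can only be supportive, and its mortality figure may be less favourable.

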15.1.1 Analysis sets

15.1.1.1 Intent-to-treat analysis set

Regardless of whether or not the study procedure was given, or whether or not the study device was implanted, the intent-to-treat (ITT) analysis set is defined as an analysis population consists of all subjects enrolled in this clinical trial.

15.1.1.2 As-treated analysis set

A subject population consisting of subjects who were enrolled in this clinical trial and implantation of the study device was initiated is defined as as-treated (AT) analysis set. The time when invasion such as incision was made on the access site is regarded as the start of the study procedure. The primary endpoint and secondary safety and efficacy endpoints will be analyzed in the AT analysis set.

